4.1 Ethics

This study will be conducted in accordance with the ethical principles that have their origin in the current Declaration of Helsinki and will be consistent with applicable US regulatory requirements and International Conference on Harmonization/Good Clinical Practice (ICH/GCP).

The study will be conducted in compliance with the protocol. The protocol and any amendments and the patient informed consent will receive Institutional Review Board (IRB) approval prior to initiation of the study.

Freely given written informed consent must be obtained from every patient or their legally acceptable representative prior to clinical trial participation, including informed consent for any screening procedures conducted to establish patient eligibility for the trial.

Study personnel involved in conducting this trial will be qualified by education, training, and experience to perform their respective task(s). This trial will not use the services of investigators or study personnel where sanctions have been invoked or where there has been scientific misconduct or fraud (e.g., loss of medical licensure, debarment). Investigators are responsible for the conduct of the study at their study site.

4.2 Regulatory Requirements

Before a site may enter patients, protocol-specific regulatory and other documents must be submitted to PrECOG as noted in study materials. Detailed information regarding document submission and control is provided to each site in separate study materials.

Once required documents are received, reviewed, and approved by PrECOG or their representative, a Study Reference Manual (SRM) will be forwarded to the site. Any changes to site regulatory documents must be submitted by the investigator to the responsible party in a timely manner. Initial study drug shipment will not occur until the regulatory packet is complete. No patients will begin protocol therapy without formal registration as per the process below.

4.3 Phase I and II Patient Registration

Patients must meet all of the eligibility requirements listed in Section 3 prior to registration. Treatment should begin \leq 10 working days from study entry (date of registration).

An eligibility checklist is included in Section 3. A confirmation of eligibility assessment by the investigator and/or site will be performed during the registration process.

Phase I Registration – Prior to discussing protocol entry with the patient **AND** prior to registering in the electronic data capture (eDC) system, call the assigned PrECOG Project Manager to ensure that a place on the protocol is open to the patient. An Enrollment Approval Form must be completed prior to registration.

Upon determination that a subject meets eligibility criteria, the subject will be registered in the study by site personnel via an electronic data capture (eDC) system. Confirmation of registration will be displayed in the eDC system. Detailed registration procedures and study contacts will be outlined in the SRM.

The phase II portion will be conducted using the dose and schedule selected from the phase I portion of the study. Before proceeding to phase II, the protocol will be amended to specify the final dose selected from phase I. Patients that participate in phase I will not be eligible to participate in phase II.

Phase II Registration – After it is verified by the site that the patient meets all eligibility criteria, registration will occur by entering the patient in the eDC system.

Full information regarding registration procedures and guidelines can be found in the SRM provided to your site. Correspondence regarding patient registration must be kept in the study records.

Patients must not start protocol treatment prior to registration.

4.4

Research Bone Marrow, Tissue and Blood Samples

Mandatory bone marrow and tumor tissue samples are required at baseline (if sufficient bone marrow and tumor tissue are available, submission is mandatory).

Mandatory peripheral blood samples will also be collected.

[figure not shown]
NOTE: No bone marrow biopsy/aspirate or tissue biopsy should be performed solely for the purposes of obtaining research samples.

Time points for bone marrow, tissue and blood samples are outlined in the study parameters (Section 10) and specific requirements are outlined in the correlative section of this protocol (Section 13) and the lab manual.

5. Study Design

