NOTE: Ibrutinib pre-treated patients must meet all eligibility criteria AND must have discontinued prior ibrutinib at least 3 months prior to starting study therapy.

Pretreated with ibrutinib: Yes No

If yes, does patient meet criteria above: Yes No

PHASE I COMPLETED NOVEMBER 25, 2019.

Phase II: Prior proteasome inhibitors allowed.

(Please note prior to Version 3.0 of the protocol prior proteasome inhibitor and/or Bruton's tyrosine kinase inhibitors were allowed but patients could not have been exposed to the combination of proteasome inhibitor and BTK inhibitor).

_____ 3.5 Age ≥ 18 years.

____ 3.6 ECOG performance status of 0-2 (Appendix I).

____ 3.7 Ability to understand and willingness to sign IRB-approved informed consent.

____ 3.8 Willing to provide archived tumor tissue, bone marrow (if sufficient bone marrow and tumor tissue are available) and blood samples for research (Section 13.0).

____ 3.9 Adequate organ function as measured by the following criteria, obtained \leq 2 weeks prior to registration:

- Absolute Neutrophil Count (ANC) \geq 750/mm³
ANC: _____ Date of Test: _____
- Platelets $>50,000/\text{mm}^3$
Platelets: _____ Date of Test: _____

NOTE: Platelet transfusions are not allowed within 3 days before registration to meet eligibility criteria.

- Serum Creatinine \leq 2x Upper Limit Normal (ULN)
Serum Creatinine: _____ ULN: _____ Date of Test: _____
- ALT and AST \leq 3x ULN
ALT: _____ Institution ULN: _____ Date of Test: _____
AST: _____ Institution ULN: _____ Date of Test: _____
- Total Bilirubin \leq 1.5x ULN (in the absence of previously diagnosed Gilbert's disease)
Total Bilirubin: _____ ULN: _____ Date of Test: _____

____ 3.10 Patients must not have received systemic treatment for MCL for at least 14 days prior to enrollment, except for steroids which may be used to manage acute symptoms related to disease up to 48 hours prior to starting study therapy. Radiation therapy must be concluded at least 14 days prior to enrollment.

____ 3.11 Women must not be pregnant or breastfeeding since we do not know the effects of ixazomib and ibrutinib on the fetus or breastfeeding child. All sexually active females of childbearing potential (not surgically sterilized and between menarche and 1 year post menopause) must have a blood test to rule out pregnancy within 2 weeks prior to registration.

Is the patient a woman of childbearing potential? _____ (yes/no)

If yes, Date of Test: _____ Results: _____

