9.6 Criteria for PET/CT Reporting

Patients who undergo PET/CT as part of their interim, on-treatment, and end of treatment staging assessments should be assessed according to the following scoring system.

1. No uptake above background.
2. Uptake \leq mediastinum.
3. Uptake $>$ mediastinum but \leq liver.
4. Uptake moderately greater than liver.
5. Uptake markedly higher than liver and/or new lesions.

X New areas of uptake unlikely to be related to lymphoma.

For further information regarding the Deauville scoring system, please refer to Barrington et al, J Clin Oncol 2014³⁵.

10. Study Parameters

1. All pre-study scans should be done \leq 4 weeks prior to registration.
2. All other pre-study assessments should be done \leq 2 weeks prior to registration.

Procedures	Screening	Cycle 1* (1 cycle=28 Days)				Cycle 2-Cycle 6*				Cycle 7 and Subsequent Cycles ^{12*}	Every 3 Cycles*	Off Treatment ¹⁴	Follow- Up ¹⁶
		Day 1 +/- 1 day	Day 8 +/- 1 day	Day 15 +/- 1 day	Day 22	Day 1 +/- 3 days	Day 8 +/- 3 days	Day 15 +/- 3 days	Day 22 BREAK				
Written Informed Consent	X												
Disease Characteristics ¹	X												
Medical/Surgical History	X												
Assessment of Baseline Signs & Symptoms	X												
Height	X												
Physical Exam including Weight	X	X		X		X				X ¹²		X	
Vital Signs (Temperature, Pulse, Blood Pressure)	X	X		X		X				X ¹²		X	
Performance Status	X	X				X				X ¹²		X	
CBC/Differential/Platelets ²	X	X		X	X	X ²		X ²		X ²		X	
Chemistry ³	X	X		X		X ³				X ³		X	
PT/INR	X												
Lactate Dehydrogenase (LDH)	X												
Vitamin D Level ⁴	X												
Peripheral Blood Flow Cytometry	X												
Serum Pregnancy Test ⁵	X												
PET/CT	X												
Chest/Abdomen/Pelvic MRI or CT ⁶										X ¹³		X	
Bone Marrow Aspirate and Biopsy ⁷	X											X ⁷	

Procedures	Screening	Cycle 1* (1 cycle=28 Days)				Cycle 2-Cycle 6*				Cycle 7 and Subsequent Cycles ^{12*}	Every 3 Cycles*	Off Treatment ¹⁴	Follow- Up ¹⁶
		Day 1 +/- 1 day	Day 8 +/- 1 day	Day 15 +/- 1 day	Day 22	Day 1 +/- 3 days	Day 8 +/- 3 days	Day 15 +/- 3 days	Day 22 BREAK				
Bone Marrow Conventional Cytogenetics and FISH ⁸	X												
Pathology Review with Ki67 Assessment ⁹	X												
Research Specimens ¹⁰		X ¹⁰									X ¹⁰	X ¹⁰	
Treatment Administration ¹¹		X	X ¹¹	X		X ¹¹	X ¹¹	X ¹¹		X ¹¹			
Concomitant Medication Review	X	X		X		X				X ¹²		X	
Adverse Events Assessment		X		X		X				X ¹²		X ¹⁵	
Survival Status													X

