* **Scheduled Visits:** +/-3 day window is allowed for scheduled ixazomib therapy, required tests and/or visits except as otherwise noted. Delay due to holidays, weekends, bad weather or other unforeseen circumstances will be permitted.

1 Record date of diagnosis and stage.

2 CBC with differential and platelet count which includes WBC, ANC, Platelets, Hemoglobin, and Hematocrit required as noted below.

Phase I: Days 1, 8, 15 and 22 of Cycle 1; Days 1 and 15 of Cycle 2 and Cycle 3 (patients with ANC <1000 and/or platelets <100,000/mm³ on Day 15 should have blood counts done on Day 22 for Cycle 2 and 3 only); and Day 1 of subsequent cycles. **Phase I completed November 25, 2019.**

Phase II: Days 1 and 15 of Cycle 1 for which a clinic visit is required. Patients will be required to be seen in clinic on Day 1 of Cycles 2-7, then every 3 cycles thereafter. Labs are only required on the days patients are seen in clinic.

Results known prior to treatment administration. Patients experiencing cytopenias should have additional labs drawn as clinically indicated at the discretion of the treating physician.

3 Albumin, BUN/creatinine, uric acid, sodium, potassium, chloride, glucose, calcium, alkaline phosphatase, AST, ALT, total bilirubin, and total protein. Days 1 and 15 of Cycle 1 for which a clinic visit is required. Patients will be required to be seen in clinic on Day 1 of Cycles 2-7, then every 3 cycles thereafter. Labs are only required on the days patients are seen in clinic.

NOTE: Patients with a history of hepatitis B or C must have a negative peripheral blood Polymerase Chain Reaction (PCR) and may not be positive for Hepatitis B surface antigen.

- 4 25(OH) Vitamin D level.
- 5 Required for sexually active females of child-bearing potential.
- 6 PET/CT may be substituted for CT Chest/Abdomen/Pelvis at the discretion of the investigator.
- 7 Bone Marrow Biopsy to include: Aspirate and core biopsy morphologic evaluation and flow cytometry. Bone marrow biopsy will be repeated at the time of suspected CR for patients with involvement at the time of enrollment. Optional bone marrow biopsies and aspirates will be performed as clinically indicated at the end of therapy and/or time of progression.

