11.2.10 Nursing/Patient Implications

Based on findings in animals, ibrutinib can cause fetal harm when administered to a pregnant woman. Ibrutinib caused malformations in rats at exposures 14 times those reported in patients with MCL and 20 times those reported in patients with Chronic Lymphocytic Leukemia or Waldenström's Macroglobulinemia, receiving the ibrutinib dose of 560 mg per day and 420 mg per day, respectively. Reduced fetal weights were observed at lower exposures. Advise women to avoid becoming pregnant while taking ibrutinib. If this drug is used during pregnancy or if the patient becomes pregnant while taking this drug, the patient should be apprised of the potential hazard to a fetus.

Women who are nursing are not eligible for this study and any woman who becomes pregnant over the course of the study will be removed from study therapy.

Ibrutinib is a Pregnancy Category D drug.

Please refer to the commercial package insert for full prescribing information.

12. Statistical Considerations

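### The only scheduled pregnancy test can be 28 days old at first dose: a cheap improvement, low priority

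*Protocol*

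**What the plan says.** Four parts of the protocol fix the timing.

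- **Section 3.11** (eligibility): sexually active women of childbearing potential "must have a blood test to rule out pregnancy within 2 weeks prior to registration". The reason given for excluding pregnant and breastfeeding women is "since we do not know the effects of ixazomib and ibrutinib on the fetus or breastfeeding child".
- **Section 4.3** (registration): "Patients must meet all of the eligibility requirements listed in Section 3 prior to registration", and treatment should begin no later than "10 working days from study entry (date of registration").
- **Section 10** (calendar): the row "Serum Pregnancy Test" is marked in the Screening column and nowhere else. Footnote 5 reads "Required for sexually active females of child-bearing potential"; it says who is tested and asks for no repeat.
- **Section 11.2.10**: "Based on findings in animals, ibrutinib can cause fetal harm when administered to a pregnant woman" and "Ibrutinib is a Pregnancy Category D drug".

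There are other safeguards. Section 3.12 requires two contraceptive methods or abstinence, starting before study entry and lasting until 3 months after the last dose. The note to 3.12 and Section 8.5 tell women to report a suspected pregnancy at once, and 8.5 stops treatment if pregnancy occurs.

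**The concern.** The test is there to keep a pregnant woman from being dosed, but its age limit is measured back from registration, and dosing can come 10 working days later. The two intervals add up. A test cannot show a pregnancy that began after the sample was taken, or one too early to detect on that day, so each extra day before dosing widens the period in which a pregnancy goes unseen. Stopping treatment under Section 8.5 acts only once exposure has happened. At stake is avoidable fetal exposure to a drug that the protocol itself says can cause fetal harm.

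**Working it through.** **Inputs**

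- Test to registration: 0 to 14 days (3.11).
- Registration to first dose: 0 to 10 working days (4.3).
- Counting rule: the day of a test is Day 0 (opening of Section 3), so the two intervals add directly.
- Later scheduled tests: none (Section 10 calendar and footnote 5).
- Patients still to be enrolled in Cohort A at August 7, 2020: 17 (5.2).

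The protocol states no figure for the age of the test at first dose, so there is none to reproduce.

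**Maximum age.** From any Monday-to-Friday registration, 10 working days without a holiday span exactly 14 calendar days.

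Maximum age = 14 + 14 = **28 days**, which is 28 / 14 = 2 times the limit accepted at registration.

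| Case | Maximum age at first dose |
|---|---|
| Weekday registration, no holiday | 28 days |
| Weekend registration, no holiday | 26 to 27 days |
| One public holiday in the interval (assumed) | 29 to 31 days |
| Two public holidays (assumed) | 30 to 32 days |

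Section 4.3 words the start as something that should happen, so a later start would lengthen the interval further.

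**How easily 14 days is passed.** It does not take both limits at once. Suppose the first dose falls c calendar days after registration and the test fell on one of the 15 days from 0 to 14 before it. The age exceeds 14 days for exactly c of those 15 test days. Counting every combination of test day, start day and weekday of registration equally:

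| Start after registration | Combinations over 14 days | Share |
|---|---|---|
| 0 to 10 working days | 385 of 15 × 11 × 5 = 825 | 47% |
| 0 to 5 working days | 105 of 15 × 6 × 5 = 450 | 23% |
| Always working day 10 | 70 of 15 × 1 × 5 = 75 | 93% |

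The equal weighting is an assumption. The protocol gives no distribution of test or start dates.

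**Number of women.** The protocol does not give the share of women of childbearing potential. Assuming 1% to 10%:

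- Women among the remaining patients: 17 × 0.01 = 0.17 to 17 × 0.10 = 1.7.
- Repeat tests the fix would trigger: 0.17 × 0.233 = 0.04 to 1.7 × 0.933 = 1.59.

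**After the fix.** The maximum age at first dose falls from 28 days to 14.

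**The case against.** The strongest reply is that nothing here is inconsistent. Sections 3.11, 4.3 and 10 all time screening work to registration, and no sentence promises a test under 14 days old at first dose; that benchmark carries the 3.11 limit over to a different date. The days that take the test from 14 to 28 lie after registration, when contraception or abstinence under 3.12 already applies, so conception then would need contraceptive failure or non-adherence. A provider also sees the patient before the first in-clinic ixazomib dose (6.3). With so few women likely to be involved, fetal exposures avoided would be only a small fraction of an already small number. Finally, the fix is partial: a 14-day-old test stays acceptable, and treatment until progression continues without scheduled testing.

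Most of this stands. It makes the point a design choice that could be better rather than an error, and it sets the priority low. It does not remove the gap: the protocol already asks for a test on top of contraception, so it does not treat contraception as a substitute, and a provider assessment is not a pregnancy test.

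A reader might also infer that the first dose is equally unguarded on blood counts, since Section 6.4 starts at Cycle 2 and the rules in Table 6-3 leave out Cycle 1 Day 1. That does not carry over. A blood count is drawn on Cycle 1 Day 1 and its result must be known before dosing (Section 10, footnote 2), so the provider decides on current values. Low counts may also come from marrow disease, where treating can be better than waiting.

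**Conclusion.** The point holds as a low-priority safety improvement. Under the protocol as written, the only scheduled pregnancy test can be 28 days old at first dose in the ordinary no-holiday case. That figure rests only on the stated windows and the calendar.

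The remaining figures rest on assumptions: the 47% (range 23% to 93%) on evenly spread dates, and the 0.2 to 1.7 women on a 1% to 10% share. A reader might take the 47% as the proportion of women who will be dosed on an old test; the documents hold no data on actual intervals, so it shows only that the situation does not need extreme timing. Nor do the documents support saying that the protocol breaches a limit of its own or contradicts itself. Fetal exposures avoided cannot be estimated from the documents. Sample size, power and type I error are not touched.

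**What to change.** Leave Section 3.11 as it is, because every Section 3 criterion has to be met before registration. In Section 10:

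1. Add a Cycle 1 Day 1 entry to the serum pregnancy test row.
2. Add to footnote 5: *If the negative test is more than 14 days old at first dose, repeat it with the Cycle 1 Day 1 bloods (the +/- 1 day window applies); it must be negative before dosing.*

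The 14 days is the 2-week limit of 3.11 measured to first dose instead of to registration. The one-day window lets the sample be taken the day before, so that the result is back in time.

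Cost: one calendar entry, one sentence, and an occasional repeat assay (0.04 to 1.6 in all under the assumptions above) on blood already drawn that day, with no added visit. The repeat shortens the period in which a pregnancy could go unseen but does not remove it. No change to the blood-count rules is proposed.

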5.1 Phase I

The phase I portion of the study will accrue patients in a standard 3+3 design with the primary objective of determining the maximum tolerate dose (MTD)/recommended phase 2 dose (RP2D) of this combination in MCL. Both ibrutinib-pretreated and ibrutinib-naïve patients will be enrolled. Planned dose levels are described below. There will be no dose escalation above Dose Level 2. If dose level 1 is too toxic, we will de-escalate to dose level (-1). There shall be no dose reductions below dose level (-1).

Dose Level	Ixazomib Days 1, 8, 15 of a 28 Day Cycle	Ibrutinib Days 1-28 of a 28 Day Cycle
-1	3 mg	420 mg
1 Starting Dose	3 mg	560 mg
2	4 mg	560 mg

NOTE: For the phase I portion of the study, ibrutinib pre-treated patients must meet all eligibility criteria AND must have discontinued prior ibrutinib at least 3 months prior to starting study therapy.

Three patients were enrolled to Dose Level 1 with no DLTs during the 28 day assessment period. Nine patients were enrolled to Dose Level 2. Five of the nine patients completed the 28 day assessment period with no DLTs, and one patient experienced a Grade 3 lung infection that was considered a DLT. Three of the nine patients were not evaluable for DLT and were replaced. One patient was inadvertently given neulasta prior to receiving Cycle 2, Day 1 therapy; another patient unintentionally took Day 15 ixazomib on Day 9; and one patient forgot to take ibrutinib the last 8 days of Cycle 1 unrelated to any toxicities. **Phase I was completed November 25, 2019. Dose Level 2 is the recommended Phase 2 dose.**

[figure not shown]
5.2 Phase II

Once dose escalation and de-escalation has completed with determination of the MTD/RP2D (**Phase I completed November 25, 2019**), the phase II portion of the study will begin. Patients will be enrolled to two cohorts, based on prior BTK inhibitor treatment: BTK-pretreated and BTK-naïve (**see below**). Patients will be treated until disease progression or until unacceptable toxicity, with dose modifications and delays as described in Section 6.5.

August 7, 2020: Phase II opened December 17, 2019 with Cohort A: BTK-naïve or Cohort B: BTK-pretreated.

Enrollment to Cohort A: BTK-naïve will continue. We plan to reach our original accrual goal of 36 BTK-naïve subjects treated at the established Dose Level 2 for 31 eligible, treated patients. The Phase I BTK-naïve patients treated at Dose Level 2 will be included in the 36 patient total. Seventeen additional BTK-naïve patients will be enrolled to complete this cohort.

Enrollment to Cohort B: BTK-pretreated will close. To date, only two patients have enrolled in Cohort B.

6. Treatment Plan

6.1 Overview

This study shall be divided into phase I and phase II components. The phase I portion of the study shall be designed to evaluate the safety and tolerability of the combination of ibrutinib and ixazomib in relapsed/refractory MCL and to identify the MTD/RP2D. The phase II portion of the study will evaluate the efficacy of this combination.

6.1.1 Ixazomib Administration

Ixazomib will be administered orally. Patients should be instructed to swallow ixazomib capsules whole, with water, and not to break, chew, or open the capsules. Ixazomib should be taken on an empty stomach (no food or drink) at least 1 hour before or at least 2 hours after food. Each capsule should be swallowed separately with a sip of water. A total of approximately 8 ounces (240 mL) of water should be taken with the capsules. A Medication Diary will be provided to the patient to record each date and dose of ixazomib after Cycle 1 (Appendix III).

Missed doses can be taken as soon as the patient remembers if the next scheduled dose is \geq 72 hours for all cycles aside from Cycle 1 of the phase 1 study. Patients with dose delays in Phase I, Cycle 1 shall be managed as described below in Section 6.2 and Section 6.2.1. A double dose should not be taken to make up for a missed dose. If the patient vomits after taking a dose, the patient should not repeat the dose but should resume dosing at the time of the next scheduled dose.

Patients on Cycle 2 and beyond of the phase I study and those enrolled on the phase II study shall not make up any ixazomib doses that are delayed >72 hours due to toxicity.

